5.1.1 Study duration per subject and definition for start/end of study

The maximum possible study duration is 68 days and the maximum period of BRV administration is 44 days including a minimum of 1 dose of iv BRV.

The start of the study is defined as the date the first Informed Consent form (ICF)/Assent form is executed. The end of the study is defined as the date of the last visit of the last subject enrolled.

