6 SELECTION AND WITHDRAWAL OF SUBJECTS

6.1 Inclusion criteria

To be eligible to participate in this study, all of the following criteria must be met:

1. Subject or the parent(s) or legal representative of the subject has signed and dated an Institutional Review Board (IRB)/Independent Ethics Committee (IEC) approved written ICF. The ICF or a specific Assent form, where required, will be signed and dated by minors.
2. The Investigator considers the subject/legal representative to be reliable and able to comply with all study requirements.
3. Subject is male or female from ≥ 1 month to <16 years of age. For subjects who are <1 year from birth and who were preterm infants, the corrected gestational age should be used for this entry requirement. The corrected gestational age is calculated by subtracting the number of weeks born before 37 weeks of gestation from the chronological age.
4. Subject weighs ≥ 3 kg (6.6lbs).
5. Subject has a diagnosis of epilepsy.
6. Subject is an acceptable candidate for venipuncture and iv infusion.
7. Subject being treated with ≥ 1 AED (including BRV) without a change of dose regimen for at least 7 days prior to Screening.
8. Subject is not being treated with vagus nerve stimulation (VNS), OR the subject is being treated with VNS and the settings have been constant for ≥ 7 days prior to Screening.
9. For female subjects, the subject is
 - Not of childbearing potential
 - OR-
 - Of childbearing potential, and
 - Is not sexually active
 - Has a negative pregnancy test
 - OR-
 - Of childbearing potential, and
 - Is sexually active
 - Has a negative pregnancy test

- Understands the consequences and potential risks of inadequately protected sexual activity, understands and properly uses contraceptive methods, and is willing to inform the Investigator of any contraception changes. Medically acceptable contraceptive methods for the study include, but are not limited to:
 - Oral or depot contraceptive treatment with at least ethinylestradiol 30µg per intake or ethinylestradiol 50µg per intake if also taking one of the following: carbamazepine, phenobarbital, primidone, phenytoin, oxcarbazepine, St. John's Wort, or rifampicin.
 - Barrier contraception: Intra Uterine Device, diaphragm with spermicide, male or female condom with spermicide
 - Abstinence from sexual intercourse

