8.3 Visit 3 (Day 1) through Visit 12 (Day 6)

- Inclusion/exclusion criteria (Visit 3 only; prior to iv BRV administration)
- Concomitant medications including AEDs
- Physical examination (brief) (at Visit 3 prior to the initial dose of BRV and daily thereafter, ideally after the morning dose of BRV each day)
- Tanner staging at Visit 3 prior to iv BRV administration only. The Investigator should use clinical judgment in deciding which subjects are selected for evaluation of Tanner Stage (ie, those subjects who are pubescent).
- Neurological examination (brief) (at Visit 3 prior to iv BRV administration and daily thereafter, ideally after the morning dose of BRV each day)
- Body weight (Visit 3 only, prior to iv BRV administration)
- Body height
- Vital signs (BP, pulse rate, RR, and temperature) (see [Table 5-2](#) and [Table 5-3](#) for timing relative to initiation of iv BRV administration). The criteria for BP values to be low or high PCS values are described in [Table 10-6](#).
- 12-lead ECG (see [Table 5-2](#) and [Table 5-3](#) for timing relative to initiation of iv BRV administration)
- Pregnancy testing for females of childbearing potential (urine test) (Visit 3 only, prior to iv BRV administration)
- AEs
- Withdrawal criteria
- C-SSRS (for subjects ≥ 6 years of age); version per [Section 10.3.3](#) (Visit 3 prior to iv BRV administration and, for subjects who receive ≥ 2 doses of iv BRV and who will enter the Down-Titration Period, at their final visit of the iv PK Period [Visit 4 to 12, as applicable])
- PK sampling (see [Table 5-2](#) and [Table 5-3](#) for timing relative to initiation of iv BRV administration)
- Collect oral BRV (as needed for IOB subjects who will enter the long-term, open-label study)
- Dispense oral BRV (at final visit of this period and only for subjects who will enter the Down-Titration Period)
- iv BRV administration

Subjects who are continuing into the long-term, open-label study after their final dose of iv BRV, will re-enter (OLB subjects)/enter (RxB, IOB, and IIB subjects) that study at the completion of assessments associated with the final iv dose of iv BRV.

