## **10.5 Vital signs, physical findings, and other observations related to safety**

### **10.5.1 Vital signs and body weight**

Vital signs (systolic blood pressure [SBP], diastolic blood pressure [DBP], respiratory rate [RR], temperature, pulse rate) and body weight will be collected according to the protocol schedule of study assessments.

Observed values of body weight will be summarized for each visit by infusion duration, and by subject group for the SS-iv.

Observed values of SBP, DBP, RR, temperature and pulse rate will be summarized for each time point (as defined in [Section 4.8](#)) within each visit. Change from Baseline for SBP, DBP, RR, temperature, and pulse rate will be summarized for all post-Baseline time points within each visit. Tables will be provided overall and by age cohort, for all subjects and by infusion duration, and by subject group for the SS-iv. Observed values for SBP, DBP, RR, temperature, and pulse rate at each timepoint will be plotted as a line for each subject in line graphs by visit (Visit 1 to 3, then for each visit individually i.e. Visit 4, 5, etc), age cohort and infusion duration. Abnormal values defined by the PCST criteria will be marked using symbols.

Vital signs PCS/PCST definitions are located in [Appendix 12.2.4](#). Vital signs PCST events (i.e. Treatment-emergent vital signs PCS) are defined as events which started on or after the first BRV medication taken during the EP0065 study that meet PCS criteria. Subjects who began the study on BRV treatment (OLB and RxB subjects) will be assumed to have taken BRV treatment on the first day of screening. Therefore, timing of a PCS being treatment emergent (i.e. a PCST) varies by subject group: all PCS are treatment emergent for RxB and OLB subjects; all PCS on or after the IOB Treatment Period are treatment emergent for IOB subjects; all PCS on or after the iv PK Period are treatment emergent for IIB subjects.

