All vital signs measurements (scheduled and unscheduled) which are taken after the first BRV medication during the EP0065 study will be assessed to determine if they meet PCST criteria. The number and percentage of subjects that meet the criteria for any PCST value, a high PCST value and a low PCST value at each timepoint and visit will be presented for each variable individually overall and by age cohort for all subjects and by infusion duration. A separate summary will be presented by country of enrollment (Hungary and rest of the World) for all subjects and by infusion duration. Percentages will be relative to the number of subjects with a value at each corresponding timepoint or visit.

The number of occurrences of each unique PCST type will be tabulated by timepoint within each visit for each subject, and include relevant criteria: gender, age, race, timepoint, visit, subject group and infusion duration. In addition, the number of subjects with at least one PCST will be displayed for each age cohort.

A subject data listing of all vital sign values will be presented. The listing will contain columns indicating which values met the criteria for PCS and PCST. All body weight values will be listed and will contain a column indicating the PCS and PCST criteria.

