### 12.2.4 Vital Signs

Parameter	Age Range	PCS Criteria
Pulse Rate (beats/minute)	<6m	<100 >180
	6m - <3y	<90 >150
	3y - <12y	<60 >130
	12y - <17y	<50 >120
	≥17y	<50 and a decrease from Baseline of ≥15 >120 and an increase from Baseline of ≥15
Systolic Blood Pressure (mmHg)	<6m	<60 >100

Parameter	Age Range	PCS Criteria
	6m - <3y	<70 >120
	3y - <12y	<80 >140
	12y - <17y	<90 >160
	≥17y	≤ 90 and a decrease from Baseline of ≥20 ≥ 180 and an increase from Baseline of ≥20
Diastolic Blood Pressure (mmHg)	<6m	<40 >65
	6m - <3y	<45 >75
	3y - <12y	<50 >80
	12y - <17y	<50 >105
	≥17y	<50 and a decrease from Baseline of ≥15 >105 and an increase from Baseline of ≥ 15
Respiratory Rate (breaths/minute)	<6m	<25 >55
	6m - <3y	<20 >45
	3y - <12y	<15 >35
	≥12y	<10 >25

Parameter	Age Range	PCS Criteria
Temperature	>1m	>101 0F (38.3 0C)
Body Weight	1m - <17y	Outside of <3% to >97% percentile of the normal body weight based on gender and the age of subject on date of weight assessment a
	≥17y	≥ 10% change from Baseline (an increase or a decrease) a

Abbreviations: m = month, y = year. A month is defined as 30 days; a year is defined as 365.25 days.

a source: <http://www.cdc.gov/growthcharts/>

This document cannot be used to support any marketing authorization application and any extensions or variations thereof.

REDACTED COPY

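### The body-weight PCST flag labels pre-infusion body size as treatment-emergent in OLB, RxB and IOB children

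*SAP*

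**What the plan says.** SAP 10.5.1 ends with the weight listing: "All body weight values will be listed and will contain a column indicating the PCS and PCST criteria". The criterion is in SAP Appendix 12.2.4. From 1 month to under 17 years it reads "Outside of <3% to >97% percentile of the normal body weight based on gender and the age of subject on date of weight assessment". Only from 17 years does it become a change rule: "≥ 10% change from Baseline (an increase or a decrease").

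SAP 10.5.1 makes treatment emergence depend on subject group. OLB and RxB subjects are taken to be on BRV from the first day of Screening, so "all PCS are treatment emergent for RxB and OLB subjects". For IOB subjects, PCS values count from the IOB Treatment Period onward. For IIB subjects, they count from the iv PK Period onward.

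The protocol schedules weight at Visit 1 (8.1), at Visit 2 for IOB subjects before oral BRV is dispensed (8.2), and in the iv PK Period as "Body weight (Visit 3 only, prior to iv BRV administration") (8.3). Visit 13 (8.6) and Table 5-4 list height but not weight. The Unscheduled Visit list (8.8) also omits weight. SAP 3.4 defines Baseline weight as the last assessment before the first infusion.

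**The concern.** A treatment-emergent flag should mark something that arose or changed on treatment. This one takes a child's size for age and the subject group as inputs, and no scheduled weight measured after an infusion. A child who has always been small or large is flagged if enrolled as OLB, RxB or IOB. The same child enrolled as IIB may not be. For OLB and RxB children, one Visit 3 weight can be both the Baseline value and a treatment-emergent abnormality.

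At stake is the reading of a safety listing. Habitual size would appear under a drug-effect label, and an empty column for IIB children could be taken as reassurance when nothing was measured.

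**Working it through.** The plan states no figure for this flag, so there is none to reproduce. The check sets the schedule against the rules and then sizes the artefact.

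**1. Which criterion applies.** Entry (Protocol 6.1): "Subject is male or female from ≥ 1 month to <16 years of age". Duration (Protocol 5.1.1): "The maximum possible study duration is 68 days". The oldest possible age on study is below 16 + 68/365.25 = 16.19 years. Nobody reaches 17, so the change rule is never used and only the percentile applies.

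**2. Scheduled weights after the first infusion.** Visit 1, Visit 2 and pre-dose Visit 3 all come before it. Visits 4 to 12 and Visit 13 have no weight. The count is 0 in every subject group.

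**3. Schedule against group rule.**

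| Group | Scheduled weights | Can be flagged PCST |
|---|---|---|
| OLB, RxB | Visit 1, Visit 3 | Both |
| IOB | Visit 1, Visit 2, Visit 3 | Visit 3 (after 2 to 10 days of oral BRV, before iv BRV) |
| IIB | Visit 1, Visit 3 | None, if the iv PK Period starts at the date and time of first iv BRV (SAP 3.2.5) |

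On schedule, the Visit 3 weight is also Baseline under SAP 3.4.

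**4. Contrast within the SAP.** For laboratory values, 10.4.1 counts a PCST only if the criterion is met at Visit 13 and was not met at Baseline. Requiring a weight after the first infusion that meets the criterion, when Baseline did not, would leave 0 scheduled weights eligible in all four groups. The flags in step 3 would disappear.

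**5. Scale, as a ceiling.** The documents give neither the weight distribution nor the mix of subject groups. Assume that all n children are OLB or RxB, that they are independent, and that a share p lies outside the percentiles. Treat the Visit 1 and Visit 3 weights, at most days apart, as one chance of being flagged. The definition gives p = 0.03 + 0.03 = 0.06 in a reference population. Expected flags = np; chance of at least one = 1 − (1 − p)^n.

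- n = 12: 12 × 0.06 = 0.72 expected; 1 − 0.94^12 = 0.524
- n = 24: 24 × 0.06 = 1.44 expected; 1 − 0.94^24 = 0.773
- n = 50: 50 × 0.06 = 3.0 expected; 1 − 0.94^50 = 0.955 to three decimals (0.9547, so 95%)

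If p were 0.10 to 0.30 (assumption), the chance of at least one in 12 would be 0.718 to 0.986, and 5 to 15 of 50 would be flagged. These figures are also ceilings. None depends on any effect of iv BRV, because the weights precede it.

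**The case against.** The strongest case against the point is that the only certain output is one column in a listing. SAP 10.5.1 names body weight apart from the vital signs and describes the two listings in separate sentences. Its PCST tables are written for vital-sign measurements. The listing that links TEAEs to earlier PCST values (10.2.2) names vital signs, ECG and laboratory values, not weight. A reader might infer that weight flags inflate the per-cohort count of subjects with a PCST. The documents do not establish that. Only the filing of weight under Vital Signs in Appendix 12.2.4 points that way, so the matter is ambiguous.

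Second, PCST is defined from the first BRV in the study, oral or iv, and the SAP change log (13.3) shows that the OLB/RxB rule was deliberate. It also covers blood pressure, pulse and ECG. That is fair, but those variables are measured after infusions and weight is not. The same paragraph of 10.5.1 first requires the event to have started on or after the first BRV dose, which habitual size does not satisfy. The group rule then overrides this for OLB and RxB.

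Three further inferences go too far:

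- **That the flag can never respond to iv BRV.** This holds for scheduled weights only. Protocol 8.8 allows extra assessments at an Unscheduled Visit, and a weight taken then could cross a percentile.
- **That the IIB result is zero by construction.** This needs the date-and-time start in SAP 3.2.5. SAP 5.1 counts the iv PK Period as started by attending Visit 3, and Table 5-1 places the Visit 3 weight in that period. On that reading, IIB children could be flagged on a pre-dose weight too. Similarly, 3.2.5 starts the IOB Treatment Period by date without a time, so a Visit 2 weight on that date might also qualify.
- **That an absent-at-Baseline condition would not help.** Applied as in the laboratory rule, it removes the false flags. The flag is then empty but no longer misleading.

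**Conclusion.** The point stands as a wrong label under a stated rule. For every age in the study the body-weight PCST is a fixed size percentile, and every scheduled weight precedes the first infusion. The rule still marks OLB and RxB children (Visit 1 or 3) and IOB children (Visit 3) as treatment-emergent. The IIB contrast rests on the SAP 3.2.5 start time, and only a discretionary unscheduled weight could reflect iv BRV.

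The consequence is limited. The weight listing is certainly affected, the PCST counts and the TEAE-PCST listing possibly, and no primary variable. The figures in step 5 of the working show scale only. They are an upper bound that assumes an all-OLB/RxB population, and they are not a forecast. The change is worth making because it is nearly free.

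**What to change.** In SAP 10.5.1 and Appendix 12.2.4:

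- Remove the PCST flag for body weight and keep the percentile flag as PCS only, described as a subject characteristic before iv BRV.
- State that weight is excluded from the PCST counts and from the listing that links TEAEs to earlier PCST values.
- State that no weight after an infusion is scheduled, so no treatment-emergent weight result is reported.

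An equivalent route is to apply the laboratory logic: criterion met after the first infusion and not at Baseline. No scheduled weight is then eligible, and the SAP should say so.

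The cost is a few sentences and one parameter taken out of the PCST programming. It needs no new data and no protocol amendment.

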## 10.5.2 Electrocardiograms (ECGs)

Standard 12-lead ECGs (heart rate, RR-interval, PQ/PR interval, QRS duration, QT interval, QTcB interval) will be performed throughout the study, according to the protocol schedule of assessments. The QTcF interval will be calculated using the following formula:

$$QTcF = \frac{QT}{\sqrt[3]{RR}}$$

Observed values of ECG parameters will be summarized for each timepoint within each visit. Change from Baseline for ECG parameters will be summarized for all post-Baseline timepoints within each visit. Tables will be provided overall, and by age cohort for all subjects, and by infusion duration, and subject subgroup for the SS-iv. Values for all ECG parameters at each timepoint will be plotted as a line for each subject in line graphs by visit (Visit 1 to 3, then for each visit individually i.e. Visit 4, 5 etc.), age cohort, and infusion duration. Abnormal values are defined by the PCS/PCST criteria (see [Appendix 12.2.5](#)) and will be displayed using symbols. ECG PCST events (i.e. Treatment-emergent ECG PCS) are defined as events which started on or after the first BRV medication taken during the EP0065 study that meet PCS criteria. In subjects who began the study on BRV treatment (OLB and RxB subjects), they will be assumed to have taken BRV treatment on the first day of screening. Therefore, timing of a PCS being treatment emergent (i.e. a PCST) varies by subject group: all PCS are treatment emergent for RxB and OLB subjects; all PCS on or after the IOB Treatment Period are treatment emergent for IOB subjects; all PCS on or after the iv PK Period are treatment emergent for IIB subjects.

All ECG parameter measurements (scheduled and unscheduled) which are taken after the first BRV medication during the EP0065 study will be assessed to determine if they meet PCST criteria. The number and percentage of subjects that meet the criteria for PCST at each timepoint and visit will be presented for each variable individually overall and by age cohort for all subjects and by infusion duration. A separate summary will be presented by country of enrollment (Hungary and rest of the World) for all subjects and by infusion duration. Percentages will be relative to the number of subjects with a value at each corresponding timepoint or visit.

The number and percentage of subjects with normal, abnormal not clinically significant, and abnormal clinically significant ECG findings, as assessed by the investigator, will be summarized for all timepoints within visits overall and by age cohort for all subjects and by infusion duration.

Shift tables will display the number and percentage of subjects having the same and different ECG finding (normal/abnormal not clinically significant/abnormal clinically significant) at each post-iv timepoint compared to their pre-iv ECG finding in the same visit, for all subjects and by age cohort, by infusion duration. Therefore, for subjects on bolus the shift from pre-iv BRV to ≤2, 5, 15, 30, 60 minutes and 2 hr after initiation of iv BRV result will be displayed, and for subjects on 15 minutes infusion the shift from pre-iv BRV to 5, 10, 15, 30, 60 minutes and 2 hr after initiation of iv BRV result will be displayed.

A subject data listing will be provided for 12-lead ECG results and will contain a column indicating the PCS and PCST criteria if a subject had abnormal ECG value. A separate listing will be provided, displaying the 12-lead ECG findings including a record of whether each finding was clinically significant or not.

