### 3.2.5 Analysis periods

This study consists of a Screening Period, an IOB Treatment Period, an iv PK Period, a Follow-up Period and a Safety (BRV-free) Period, see [Section 2.3](#) for more details on these periods.

Start of Screening Period is defined as the date of enrollment and end of Screening Period is defined as immediately before first allocated BRV treatment.

Start of IOB Treatment Period is defined as the date of first allocated oral BRV treatment and end of IOB Treatment Period is defined as immediately before first iv BRV treatment.

Start of iv PK Period is defined as the date and time of first allocated iv BRV treatment and end of iv PK Period is defined as 12 hours after start of last iv BRV treatment.

Start of Follow-up Period is defined as 12 hours after start of last iv BRV treatment and end of Follow-up Period is defined for the following scenarios:

- Subjects who transition study: as TC-1
- Subjects who do not transition and do not down-titrate: as end of study
- Subjects who down-titrate: as 12 hours after start of last down-titration treatment.

Only subjects who down-titrate have a Safety (BRV-free) Period. Start of Safety Period is defined as immediately after the end of Follow-up Period (>12 hours after start of last down-titration treatment) and end is defined as end of study.

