### 3.4 Definition of Baseline values

Baseline for laboratory variables (blood chemistry, hematology, and endocrinology), vital signs, body weight, and quantitative electrocardiography (ECG) variables is defined as the latest assessment prior to the first infusion of iv BRV. Both scheduled and unscheduled assessments from the central laboratory are considered.

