**12.2.5 ECG**

Parameter	PCST Criteria
QT interval	For $\geq 17$ y: $\geq 500$ ms or $\geq 15\%$ increase from baseline
QTc interval	For $< 17$ y: $\geq 440$ ms or $\geq 15\%$ increase from baseline For $\geq 17$ y: $\geq 450$ ms or $\geq 60$ ms increase from baseline
PR interval	For 1 m to $< 6$ m: $\geq 145$ ms or $\geq 25\%$ increase from baseline For 6 m to $< 3$ y: $\geq 155$ ms or $\geq 25\%$ increase from baseline For 3 y to $< 11$ y: $\geq 170$ ms or $\geq 25\%$ increase from baseline For 11 y to $< 17$ y: $\geq 175$ ms or $\geq 25\%$ increase from baseline For $\geq 17$ y: $\geq 200$ ms or $\geq 25\%$ increase from baseline
QRS interval	For 1 m to $< 7$ y: $\geq 78$ ms or $\geq 25\%$ increase from baseline For 7 y to $< 17$ y: $\geq 88$ ms or $\geq 25\%$ increase from baseline For $\geq 17$ y: $\geq 100$ ms or $\geq 25\%$ increase from baseline
HR	For 1 m to $< 12$ m: $\leq 110$ bpm and a decrease of $\geq 20$ bpm from baseline or $\geq 180$ bpm and an increase of $\geq 20$ bpm from baseline For 12 m to $< 3$ y: $\leq 90$ bpm and a decrease of $\geq 20$ bpm from baseline or $\geq 150$ bpm and an increase of $\geq 20$ bpm from baseline For 3 y to $< 12$ y: $\leq 65$ bpm and a decrease of $\geq 20$ bpm from baseline or $\geq 130$ bpm and an increase of $\geq 20$ bpm from baseline For 12 y to $< 17$ y: $\leq 60$ bpm and a decrease of $\geq 20$ bpm from baseline or $\geq 120$ bpm and an increase of $\geq 20$ bpm from baseline For $\geq 17$ y: $\leq 50$ bpm and a decrease of 20% from baseline or $\geq 120$ bpm and an increase of 20% from baseline

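### For subjects already on oral BRV, the Visit 1 ECG is tested for change against a Baseline recorded later, so a fall before any infusion can be flagged as a treatment-emergent increase (minor)

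*SAP*

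**What the plan says.** **Baseline.** For ECG and vital signs, SAP 3.4 says Baseline "is defined as the latest assessment prior to the first infusion of iv BRV". Protocol Tables 5–2 and 5–3 schedule an ECG within the hour before each infusion, so Baseline is normally the Visit 3 pre-infusion ECG. The Visit 1 ECG (protocol 8.1) is earlier.

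**What is tested.** SAP 10.5.2: "All ECG parameter measurements (scheduled and unscheduled) which are taken after the first BRV medication during the EP0065 study will be assessed" to see whether they meet PCST criteria. OLB and RxB subjects are taken to be on BRV from the first day of Screening, and "all PCS are treatment emergent for RxB and OLB subjects".

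**The criteria.** In SAP 12.2.5, below 17 years, QTc, PR and QRS each qualify on an absolute limit or on a percentage "increase from baseline" (15% for QTc, 25% for PR and QRS). Heart rate needs a limit and a change together, for example at or above a threshold "bpm and an increase of" at least 20 bpm.

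**Where a time limit is written.** SAP 10.5.2 does restrict the change summaries: "Change from Baseline for ECG parameters will be summarized for all post-Baseline timepoints within each visit". The sentence on PCST assessment carries no such restriction.

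**Vital signs.** SAP 10.5.1 uses the same emergence rule. For subjects initiating BRV intravenously, "all PCS on or after the iv PK Period are treatment emergent for IIB subjects", and SAP 3.2.5 adds: "Start of iv PK Period is defined as the date and time of first allocated iv BRV treatment". Section 10.5.1 also asks for the number of subjects with at least one PCST, by age cohort only.

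**The concern.** Version 4.0 of the SAP (13.3) made every PCS value in OLB and RxB subjects treatment-emergent. That moved the start of emergence back to Screening, while Baseline stayed at the first infusion. For limits on absolute values the mismatch does no harm. For limits on change, a Visit 1 value is measured against a reference that did not yet exist, and the sign of the change is reversed.

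At stake is the correctness of individual ECG flags. A shortening QTc, PR or QRS before any iv dose would appear in the Visit 1 row of the ECG PCST table, in the plots and in the listings as an emergent prolongation. The same can happen to an unscheduled ECG taken in an OLB, RxB or IOB subject after first BRV but before the Baseline ECG.

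The vital-sign criteria for pulse, blood pressure, respiratory rate and temperature are absolute below 17 years (SAP 12.2.4), so direction is not an issue there. The lesser point is that the per-cohort count combines pre- and post-infusion readings for OLB, RxB and IOB but only post-infusion readings for IIB, in a study whose objective concerns iv BRV.

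**Working it through.** The study is descriptive and the plan states no figure on this point, so there is nothing to reproduce. The rules were applied literally.

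**1. Fall that triggers a flag.** Let V be the Visit 1 value, B the Baseline and c the percentage limit. The rule flags V when (V − B)/B ≥ c, that is, when the fall from V to B is at least 1 − 1/(1 + c).
- QTc, c = 0.15: 1 − 1/1.15 = 13.0%.
- PR and QRS, c = 0.25: 1 − 1/1.25 = 20.0%.

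**2. Examples.** The QTc, PR and QRS Visit 1 values are below their absolute limits.

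| Parameter (age) | Visit 1 | Baseline | Change as scored | Actual course | Flag |
|---|---|---|---|---|---|
| QTc (<17 y, limit 440 ms) | 430 | 370 | +16.2% | −14.0% | increase |
| PR (3 to <11 y, limit 170 ms) | 165 | 130 | +26.9% | −21.2% | increase |
| QRS (7 to <17 y, limit 88 ms) | 85 | 68 | +25.0% | −20.0% | increase |
| HR (3 to <12 y, ≥130 and rise ≥20) | 132 | 110 | +22 bpm | −22 bpm | increase |
| HR (3 to <12 y, ≤65 and fall ≥20) | 64 | 90 | −26 bpm | +26 bpm | decrease |

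In the opposite order, QTc 370 then 430 ms is a real rise of 16.2%, and the Visit 1 value is not flagged. The percentage rule acts alone for QTc when Baseline is below 440/1.15 = 382.6 ms.

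**3. ECGs affected.** Scheduled ECGs for an OLB/RxB subject with one infusion: Visit 1, Visit 3 pre-infusion and 6 post-initiation, 8 in all. A second infusion adds 1 + 6, making 15. One of them, Visit 1, is tested backwards (1 of 8, or 1 of 15). IOB subjects have no scheduled ECG at Visit 2, so only an unscheduled one could be affected. If no later pre-infusion ECG exists, Visit 1 is itself Baseline and the problem does not arise.

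**4. How often, with no true change.** The documents give no within-subject variability, so the coefficient of variation (CV) is assumed. For lognormal readings, P(V/B ≥ 1 + c) = 1 − Φ(ln(1 + c)/(σ√2)), with σ² = ln(1 + CV²).
- QTc, 15%: 0.05% at CV 3%, 2.4% at CV 5%. These include values already at or above 440 ms, which are flagged anyway.
- QTc flags added below 440 ms, by simulation with assumed mean 390 to 420 ms and between-subject SD 15 to 20 ms: about 0.01 to 0.04% of OLB/RxB subjects at CV 3%, 0.6 to 2% at CV 5%, and 4 to 10% at CV 10%.
- PR or QRS, 25%, upper bound: 0.08% at CV 5%, 5.7% at CV 10%.

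If all 12 subjects of a cohort were OLB/RxB (the share is not given), the upper QTc figures mean 12 × 0.02 = 0.24 subjects at CV 5% and 12 × 0.10 = 1.2 at CV 10%. No rate was estimated for heart rate.

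**5. Vital-sign count.** Scheduled pulse readings for OLB/RxB with one infusion: Visit 1, Visit 3 pre-infusion and 5 post-initiation = 7, of which 2 (29%) precede iv BRV. Blood pressure adds the 2-hour reading: 2 of 8 (25%). With two infusions these become 2 of 13 (15%) and 2 of 15 (13%). For IOB with one infusion, at least 1 of 6 (17%) and 1 of 7 (14%). For IIB, none.

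As an illustration only, assume a 5% chance of a PCS value per reading and within-subject correlation 0.3 to 0.7. Of OLB/RxB subjects counted with a pulse PCST, 15 to 21% would have it only before infusion with one infusion, and 6 to 9% with two.

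**The case against.** The best defence is that an increase from baseline ordinarily means a later change, and that 10.5.2 confines its change tables to post-Baseline timepoints. A sensible programmer may apply the criteria that way. That lowers the chance of harm, but it is not what the text says. The PCST sentence covers every ECG after first BRV, the emergence rule covers all PCS in OLB/RxB, and the restriction sits in a different sentence about different tables. For laboratory values, SAP 10.4.1 does write the anchor out: criteria met at Visit 13 and not at Baseline.

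The second defence stands in full: the effect is small and visible. The main ECG PCST table is by timepoint and visit, the plots draw Visits 1 to 3 as one line per subject so a fall is seen as a fall, and the shift tables compare each post-iv ECG finding with the pre-iv finding of the same visit.

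On vital signs, the mixed count follows from a recorded choice, and the by-timepoint table already separates the values. That stands, and makes the split an improvement rather than a correction.

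Three stronger readings are tempting and not supported.
- A reader might infer that post-infusion ECG rates are distorted. They are not: those ECGs are compared with an earlier Baseline and sit in their own rows.
- A reader might infer that counting Screening values as emergent in OLB/RxB is itself an error. It is recorded in SAP 13.3 and matches the adverse-event rule in 10.2.
- A reader might infer that the listing of TEAEs against earlier PCSTs cannot be read relative to infusion. SAP 3.2.3, 3.2.4 and 3.2.9 together let a reader place each PCST, and laboratory PCSTs are limited to Visit 13.

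**Conclusion.** Wrong as written, and minor. For OLB and RxB subjects with a later pre-infusion ECG, the literal PCST rule tests the Visit 1 ECG in reverse, and can label a pre-iv fall in QTc, PR or QRS an emergent increase; heart-rate flags can be wrong in both directions. That the rule does this is certain from the text. How often depends on variability the documents do not give: about 2% of OLB/RxB subjects or fewer for QTc at a CV up to 5%, and more only if the CV is nearer 10%. The consequence is a few wrong flags in pre-iv rows, plots and listings.

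The per-cohort vital-sign count is secondary. It is consistent with the SAP's own definition, but it cannot be read as a count after iv BRV, nor compared between IIB and the other groups.

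**What to change.** 1. In SAP 10.5.2 and 12.2.5, state that the change-from-baseline criteria apply only to ECGs recorded after Baseline. Assess earlier ECGs on the absolute QTc, PR and QRS limits alone. Assign no heart-rate PCST before Baseline, since that rule needs both a limit and a change. All the example flags above then disappear, while a Visit 1 value that meets an absolute QTc, PR or QRS limit is still reported.

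2. In SAP 10.5.1, keep the any-BRV PCST flag and show the per-cohort count of subjects with at least one vital-sign PCST also for values after the start of the first infusion.

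The cost is SAP wording, one derived variable (before or after the start of the first infusion) and one extra column. No new data are needed. The price is that an extreme heart rate at Visit 1 would appear as an observed value without a PCST flag.
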